14.0 BIOANALYTICAL PROCEDURES
The concentration of Olaparib in plasma samples will be quantified at using validated LC-MS/MS method.
14.1 Method Validation
Bioanalytical method will be validated at which is in accordance with the current regulatory guidelines on validation of bioanalytical methods.

Confidential Page 72 of 91

term stability of stock solution and internal standard).

Method validation of Olaparib in human plasma will be carried out by using analytical method developed at

effect, linearity, ruggedness, accuracy and precision (repeatability and reproducibility), percent recovery and stability of samples (freeze-thaw stability, bench-top stability, autosampler stability, short-term and long-

This analytical method will be validated for the sensitivity, specificity, matrix

### 14.2 Assay of Samples

The plasma sample will be quantified for Olaparib using a validated method. Plasma samples of patients included in the PK dataset (defined in section 15) will be analyzed.

Pharmacokinetic repeats will not be performed for this study.

The analysis of patient's samples will be done using calibration curve with quality control samples, distributed throughout each batch. The details for the preparation of the calibration curve and quality control samples and the analytical batch acceptance criteria will be discussed in the respective in-house procedure. The analyst will not have access to the randomization schedule until analysis is completed.

Incurred Study Sample Re-analysis

Incurred Study sample analysis will be performed to ensure method reproducibility as per

Note: All the activities will be performed as per the latest /updated version of bioanalytical plan for the study.

### 15.0 PHARMACOKINETICS AND STATISTICAL ANALYSIS

Pharmacokinetic and statistical analyses for plasma concentration versus time profile of Olaparib will be performed on the data obtained from patients included in the PK dataset.

### PK dataset

Data from the following patients will be included in the PK dataset:

- Patients who have completed both periods and have missed samples in any period that may not affect
  the estimation of the Cmax,ss and/or AUC parameters and have been predetermined prior to the
  bioanalytical analysis to not significantly impact the overall outcome of the study;
- Patients who complied with all protocol requirements, or encountered protocol deviations that do not
  impact the estimation of the PK parameters.

Patients withdrawn prior to sample analysis for pharmacokinetic reasons (i.e., an event that could result in an inadequately characterized pharmacokinetic profile for olaparib) will not be included in the PK and statistical analysis.

Any decision for excluding data from the final data set will be provided with a detailed explanation and will be properly recorded and dated.

PK dataset will be defined in consultation with the sponsor at different study stages for different sets of patients, prior to initiation of sample analysis for each set of patients. This dataset will be reassessed, if

required (e.g., missing concentration value due to analytical reason), upon completion of the sample analysis. The PK dataset will be finally confirmed by the sponsor prior to database lock.

### Safety Dataset

The safety dataset will include randomized patients who receive at least one dose of IMP. Data from subjects in this dataset will be used for the assessment of safety.

### 15.1 Pharmacokinetic Parameters

Pharmacokinetic parameters CmaxSS, CminSS, AUC(0-1)SS, CavSS, TmaxSS, Swing, percentage of fluctuation will be calculated using plasma concentration vs time profile (Actual time of sample collection) data of both investigational medicinal products in individual patients using Phoenix WinNonlin Software Version 8.2 or higher (Pharsight Corporation, USA).

Primary parameters:		
CmaxSS	Maximum plasma concentration during the dosing interval at steady state	
AUC(0-1)ss	Area under the plasma concentration versus time curve for one dosing interval at steady state	

Secondary Parai	meters:	
CminSS	Concentration at the end of a dosing interval	
CavSS	Average plasma concentration over the steady state dosing interval	
T maxSS	Time of maximum measured plasma concentration over the steady state dosing interval	
Swing	[C maxSS -C minSS / C minSS ]*100	
Percentage of fluctuation	[C maxSS -C minSS /C avSS ]*100	

Pharmacokinetic parameters will be calculated by non-compartmental analysis using Phoenix WinNonlin software Version 8.2 or higher (Pharsight Corporation, USA). All pharmacokinetic parameters will be estimated from the Plasma concentration time profile data.

All concentration values below the Limit of Quantification (LOQ) will be set to "zero" for all pharmacokinetic and statistical calculations. Any missing sample will be reported as "Missing" and will not be included for pharmacokinetic and statistical analysis.

Data from patients with missing concentration values (missed blood draws, lost samples, samples unable to be quantified) may be used if pharmacokinetic parameters can be estimated using the remaining data points. Otherwise, concentration data from these subjects will be excluded from the final analysis.

In case of sample collection deviations, the actual time point of sample collection will be used for the computation of pharmacokinetic parameters.

Missing plasma samples will be handled as per

### 15.2 Statistical Analysis

SAS® Software, Version 9.4 or higher will be used for statistical analysis of pharmacokinetic parameters CmaxSS and AUC(0-t)ss.

By considering the three day's morning pre-dose concentrations in a given period, steady state analysis will be performed for each subject in each period by using the linear regression analysis to obtain the p-values. The above analyses will be done using procedure PROC REG in SAS, version 9.4 or higher.

For achieving the steady state following procedure should be assessed:

[figure not shown]
Step 1: For each subject in each period the P-values should be statistically insignificant at 5% level of significance.

If, P-values are found statistically insignificant, those patients are considered to achieve steady state. If, P-values are found significant for particular subject then go for the second step. Go for second step for patients who have missing pre-dose sample for Day 6 or Day 14.

Step 2: Ratio of the pre-dose concentrations of last two pre-dose should be  $\geq 80\%$  or should be  $\leq 120.00\%$ .

In case ratio of last two pre-dose concentrations is found to be  $\geq 80\%$  or  $\leq 120.00\%$  patients will be considered to achieve steady state. If two pre-dose concentrations is found to be less than 80% or greater than 120%, patients will not be considered to achieve steady state and will be removed from bioequivalence evaluation.

Two stage design according to Potvin C: Evaluate the power at stage 1 using the variance estimate from stage 1 and an  $\alpha$  level of 0.05. If the power is greater than or equal to 80% (calculated by observed variability and GMR=0.95), evaluate BE at stage 1 using an  $\alpha$  level of 0.05 and stop whether BE is met or not. If the power is less than 80%, evaluate BE using an  $\alpha$  of 0.0294. If the BE criterion is met, stop. If the BE criterion is not met, calculate the sample size based on the variance estimated at stage 1, GMR=0.95 and an  $\alpha$  level of 0.0294 and continue to stage 2. If the ratio is outside 80.00%-125.00% then study will not proceed for stage 2. Evaluate BE at stage 2 using data from both stages and an  $\alpha$  level of 0.0294. Stop here whether BE is met or not and regardless of the power achieved.

For outlier identification, appropriate statistical tests could be performed. Outliers are defined as subjects having discordant values of one or more pharmacokinetic parameters when compared with other values, e.g., a subject differs notably from the rest of the subjects for the test product response versus the reference product response. Outlier test will be performed using appropriate statistical method as per for "Detection of Outliers". Subject data will not be removed from the statistical analysis solely based on the results of statistical outlier tests. Outlier data may only be removed from the statistical analysis if there is a real-time documentation demonstrating a protocol violation during the clinical and/or analytical phase of the BE study.

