#### 7.1 Number of Patients

Considering a maximum expected intra-patient variability of 35% based on available literature estimates, a true ratio (T/R) of 0.95, 56 evaluable patients are adequate to achieve at least 81% power at 5% level of significance to meet the bioequivalence limit of 80.00% to 125.00% at Stage 1.

Sufficient number of patients will be enrolled to have 56 evaluable patients in the Stage 1 (about, but not limited to, 70 enrolled patients) and Stage 2 sample size (if needed) will be decided on the basis of data (observed CV) obtained after the completion of Stage 1. Maximum sample size (Stage 1 + Stage 2) is expected, but not limited to, approximately 120 enrolled patients. This is a 2-stage design according to Potvin C method. Overall expected power is 86%.

Enrollment will be continued until at least 56 evaluable patients will complete the Stage 1. In case additional patients are recruited, those patients will continue the study until completion/withdrawal and be included in the pharmacokinetic and statistical analyses as applicable.

Note: Patients enrolled in Stage 1 will not be eligible for Stage 2.

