## 10.4 Sampling Schedule

A total of 43 blood samples each of 03 mL will be collected from each patient for PK assessment during the study.

The venous blood samples will be withdrawn from each patient in each period at the following timepoints:

The post dose blood samples will be collected with an allowable deviation of  $\pm$  2 minutes. In all instances, however, the exact time of dosing and of each sample collection must be recorded. Samples collected outside the scheduled time will be considered as protocol deviations.

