### 15.2.6 Bioequivalence criteria

For Stage 1 with Power  $\geq$  80%:

Based on the statistical results of 90% confidence intervals for the geometric least squares means ratio for the ln-pharmacokinetic parameters  $C_{maxSS}$  and  $AUC_{(0-r)SS}$  for Olaparib the conclusions will be drawn whether test formulation is bioequivalent to reference formulation under Fasting condition. Acceptance range for bioequivalence is 80.00%-125.00% for 90% confidence intervals of the geometric least squares means ratio of  $C_{maxSS}$  and  $AUC_{(0-r)SS}$ .

For Stage 1 with Power < 80% and for Stage 2, if required:

Based on the statistical results of 94.12% confidence intervals for the geometric least squares means ratio for

the log-transformed pharmacokinetic parameters  $C_{maxSS}$  and  $AUC_{(0-\tau)SS}$  for Olaparib the conclusions will be drawn whether test formulation is bioequivalent to reference formulation under Fasting condition. Acceptance range for bioequivalence is 80.00%-125.00% for 94.12% confidence intervals of the geometric least square means ratio of  $C_{maxSS}$  and  $AUC_{(0-\tau)SS}$ .

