4.3 PK population

Pharmacokinetic and statistical analyses for plasma concentration versus time profile of Olaparib will be performed on the data obtained from patients included in the PK dataset.

PK dataset

Page 11 of 30

Data from the following patients will be included in the PK dataset:

- Patients who have completed both periods and have missed samples in any period that may not affect the estimation of the C_{max,ss} and/or AUC parameters and have been predetermined prior to the bioanalytical analysis to not significantly impact the overall outcome of the study;
- Patients who complied with all protocol requirements, or encountered protocol deviations that do not impact the estimation of the PK parameters.

Patients withdrawn prior to sample analysis for pharmacokinetic reasons (i.e., an event that could result in an inadequately characterized pharmacokinetic profile for olaparib) will not be included in the PK and statistical analysis.

Any decision for excluding data from the final data set will be provided with a detailed explanation and will be properly recorded and dated.

PK dataset will be defined in consultation with the sponsor at different study stages for different sets of patients, prior to initiation of sample analysis for each set of patients. This dataset will be reassessed, if required (e.g., missing concentration value due to analytical reason), upon completion of the sample analysis. The PK dataset will be finally confirmed by the sponsor prior to database lock.

5. General Aspects of Statistical Analysis

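### The outlier rule lets a patient already kept in the PK dataset be removed because of her result, with no test of PK relevance and no equal treatment of others with the same violation

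*Protocol*

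**What the plan says.** Protocol 15.2 (outlier paragraph) and SAP 10 carry the same rule. An outlier is a subject with discordant PK parameter values; the example given is a test-versus-reference response that differs from everyone else's. A statistical test alone may not remove anyone. The operative sentence is "Outlier data may only be removed from the statistical analysis if there is a real-time documentation demonstrating a protocol violation", and the violation may lie in the clinical or the analytical phase. The test is set by a separate procedure on outlier detection, which the public documents do not show.

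Three other places bear on it:

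- **PK dataset** (Protocol 15.0, SAP 4.3). It keeps patients who "encountered protocol deviations that do not impact the estimation of the PK parameters". It is defined before sample analysis starts for each set of patients and reassessed afterwards if required. Every exclusion needs a detailed, recorded and dated explanation.
- **Sampling times** (Protocol 10.4 and 15.1). "Samples collected outside the scheduled time will be considered as protocol deviations". Parameters are then computed from actual times.
- **Deviations** (Protocol 16.2). A major deviation is one that may lead to withdrawal or to exclusion from the bioanalytical or statistical part. Timing deviations in blood sampling are named among the minor, logistic ones. The sponsor may reclassify a deviation with written justification, and its classification prevails. No time limit is given.

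**The concern.** Removal rests on two conditions: a discordant result and a documented protocol violation. The second condition is loose. Section 16.2 defines deviations, major and minor, but not violations. Nothing says that the violation must be able to affect CmaxSS or AUC(0-tau)SS, or must explain the odd value. Nothing extends the exclusion to a patient with the same violation and an ordinary result.

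Set this beside the PK-dataset rule. A violation that affects PK estimation should already have removed every affected patient, in most cases before any concentration was known. If it does not affect PK estimation, the patient was deliberately kept, and the outlier clause reopens that decision with her T/R in view.

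Dropping only discordant patients lowers the residual variance and narrows the confidence interval. The chance of a false bioequivalence conclusion can then exceed the value simulated for the design.

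**Working it through.** **Inputs from the documents**

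- "Considering a maximum expected intra-patient variability of 35% based on available literature estimates, a true ratio (T/R) of 0.95, 56 evaluable patients are adequate" (Protocol 7.1).
- High-power branch of stage 1: "Acceptance range for bioequivalence is 80.00%-125.00% for 90% confidence intervals", one-sided alpha 0.05. Low-power branch and stage 2: "Acceptance range for bioequivalence is 80.00%-125.00% for 94.12% confidence intervals", one-sided alpha 0.0294 (Protocol 15.2.6).
- The branch is chosen from power at the observed variance and GMR 0.95 (SAP 9.2.1). The study stops if the point estimate is outside 0.80-1.25. The Annexure simulation caps total N at 120.

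**Assumptions, because the documents give no figures**

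- Cut-off of 2 or 3 on the studentized residual r of each patient's ln(T/R) at stage 1.
- 20%, 50% or 100% of patients with an eligible violation, unrelated to PK.
- Removal before the power check; SAP 9.2.1 does not say where the outlier step falls.

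**Step 1. Reproduce the plan.** The within-patient variance is ln(1 + 0.35²) = ln(1.1225) = 0.1156, and with 56 patients the standard error of the ln ratio is √(2 × 0.1156 / 56) = 0.064. Exact TOST power in a single stage is 83.5%, consistent with "adequate to achieve at least 81% power at 5% level of significance". A Potvin C simulation (100,000 trials, single-site degrees of freedom) gives:

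- Final power 85.8%; the plan says "Overall expected power is 86" per cent.
- Stage 1 power 80.8%; the Annexure has 80.7% for standard Potvin C and 80.4% for the modified design.
- Type I error 0.0488 at true ratio 1.25. Annexure Table 2 brackets CV 35% with 0.0487 (34%) and 0.0476 (36%), reading its fifth column as n1 = 56, as in Table 5.

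**Step 2. Add selective removal.** A patient is dropped only if r passes the cut-off and she has an eligible violation. Type I error at true ratio 1.25, CV 35%:

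| Removal rule | 20% eligible | 50% eligible | 100% eligible |
|---|---|---|---|
| r beyond ±3 | 0.0495 | 0.0506 | 0.0526 |
| r beyond ±2 | 0.0557 | 0.0663 | 0.0865 |
| Single most discordant patient, beyond ±2 | 0.0550 | 0.0615 | 0.0671 |
| Unfavourable side only, r > 2 | 0.0615 | 0.0833 | 0.1298 |

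The simulation standard error is √(0.0488 × 0.9512 / 100,000) = 0.0007. The smallest rise, 0.0495 − 0.0488 = 0.0007, is therefore no larger than noise. The largest two-sided rise is 0.0865 − 0.0488 = 0.0377.

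**Step 3. Compare with removal that ignores the result.** Dropping all of a 20% group with the violation, whatever their values, gives 0.0469. The inflation comes from selecting on the result, not from losing patients.

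**Step 4. Second route.** Removal lowers the observed variance, so more trials pass the 80% power check and use alpha 0.05. With 20% eligible and a cut-off of 2, the share rises from 71.5% to 76.9%.

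**Step 5. Effect at the planning ratio.** At true ratio 0.95, two-sided removal beyond ±2 raises the stage 1 success rate from 0.808 to 0.814 (20% eligible) or 0.842 (100%). Final power does not rise: it moves from 0.858 to about 0.855.

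**Step 6. What the Annexure covers.** Its methodology section says that each step of the real evaluation must be reflected in the simulation program. It lists three modifications: point-estimate futility, a cap on total N, and reduced degrees of freedom. Outlier removal is not among them, so its finding of no inflation does not extend to this step. The R code is not shown in the public copy.

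**The case against.** The rule has real safeguards. It is a permission. A test alone removes nobody. The documentation must be made in real time, so a violation cannot be written up after the result is seen, and every exclusion must be explained and dated. The clause also has a proper use: a violation in the analytical phase cannot be known when the PK dataset is first set. The unseen outlier procedure may fix the cut-off and more. All of this stands and limits the point, but none of it requires PK relevance or equal treatment.

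Three stronger readings are tempting, and the documents do not support them.

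1. *Almost every patient is eligible, because any late sample counts.* Section 16.2 names sampling-time deviations as minor and makes exclusion from the statistics a mark of a major deviation. The ±2 minute window applies to post-dose samples. If one pre-dose draw is allowed for each of the seven sampling days, these number about 43 − 7 = 36, which matches the 36 discard volumes in Protocol 10.6; the schedule itself is not shown. With an assumed 1% or 5% miss rate per sample, 1 − 0.99^36 = 30% or 1 − 0.95^36 = 84% of patients would have one on record. That matters only if such deviations count as violations or are reclassified.
2. *The error rate reaches 13%.* That needs a cut-off of 2, every patient eligible and removal on the unfavourable side only. The text is not one-directional, so this would be misuse of the rule.
3. *The rule favours a bioequivalence conclusion in general.* At a true ratio of 0.95, two-sided removal does not raise final power.

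**Conclusion.** The gap is in the text of both documents: a patient retained under the PK-dataset rule can later be excluded because her result is discordant, while others with the same violation stay.

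Under Potvin C at CV 35%, two-sided removal gives a type I error of about 0.050-0.053 at a cut-off of 3 and 0.056-0.087 at a cut-off of 2, against 0.0488 with none. These ranges assume that 20-100% of patients are eligible, that violations are unrelated to PK and that the log data are normal. At a cut-off of 3 with few eligible patients the effect is negligible. The documents fix neither quantity, so they do not show that the 5% level fails. They show that it is not protected against this step. The point is worth correcting because the remedy is cheap.

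**What to change.** Replace the last sentence of the outlier paragraph in Protocol 15.2 and SAP 10 with a rule on these lines:

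- A patient may be removed only for a documented clinical- or analytical-phase violation that meets the PK-dataset exclusion test, meaning that it affects estimation of CmaxSS or AUC(0-tau)SS.
- The same exclusion applies to every patient with that violation, whether or not she is an outlier.
- Otherwise the patient stays in the primary bioequivalence analysis, and the analysis without outliers is reported as a sensitivity analysis only.

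The cost is about two sentences in each document. A discordant patient whose deviation is irrelevant stays in, so the confidence interval will sometimes be wider. If as many as 20% of patients shared a PK-relevant violation and all were dropped, final power at ratio 0.95 would fall from 0.858 to about 0.84. The existing PK-dataset rule should already exclude those patients, and deviations without PK impact would remove nobody.

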### 15.2.1 Analysis of variance

### For Stage 1:

The In-transformed pharmacokinetic parameters (CmaxSS and AUC(0-t)SS) will be analyzed using ANOVA model with the main effects of Center, Treatment, Period (Center), Sequence, Sequence\*Center as fixed effects and Patient (Within Sequence\*Center) as random effect.

The sequence effect will be tested at the 0.10 level of significance using the Patient (within Sequence\*Center) mean square from the ANOVA as the error term. All other main effects will be tested at the 0.05 level of significance against the residual error (mean square error/MSE) from the ANOVA as the error term.

Each analysis of variance will include calculation of least-squares means, the difference between the adjusted formulation means and the standard error associated with the difference. The above analyses will be done using procedure PROC GLM in SAS, version 9.4 or higher.

### For Stage 2:

The In-transformed pharmacokinetic parameters (CmaxSS and AUC(0-1)88) will be analyzed using ANOVA model with the main effects of Center, Stage, Treatment, Period (Center\*Stage), Sequence, Sequence\*Center\*Stage, Sequence\*Center\*Stage, as fixed effects and Patient (Within Sequence\*Center\*Stage) as random effect.

The Sequence, Stage and Center effects will be tested using the Patient (within Sequence\*Center\*Stage) effect as the error term.

The sequence effect will be tested at the 0.10 level of significance using the Patient (within Sequence\*Center\*Stage) mean square from the ANOVA as the error term. All other main effects will be tested at the 0.05 level of significance against the residual error (mean square error/MSE) from the ANOVA as the error term.

Each analysis of variance will include calculation of least-squares means, the difference between the adjusted formulation means and the standard error associated with the difference. The above analyses will be done using procedure PROC GLM in SAS, version 9.4 or higher

Note: Prior to ANOVA analysis for assessment of center effect, data from all the centers will be arranged in ascending order based on the number of evaluable patients available per center. This shall lead to center with least number of evaluable patients followed by center which has more number of evaluable patients in increasing order. This will lead to center with maximum number of evaluable patients as last center and center with least number of patients as first center. In case any center has less than five evaluable patients, data from this center will be pooled with subsequent center as per the center arrangement done as mentioned above. If there are more than one center with less than five patients in each center, the data of all this centers will be combined until five or more than five patients are available and this will be treated as separate center for further data analysis. After combining centers as mentioned above, further assessment will be done for treatment sequence available for combined center data. After combining two or more centers, at least one patient should be having TR and RT sequence each. In case same is true, centers combined will be used further for data analysis. Incase same is not observed, data combining will be continued for subsequent center as per the center arrangement done as mentioned above. This shall be continued until at least one patient for each treatment sequence TR and RT is available.

Note: Analysis of study will be performed as per latest/updated Statistical Analysis Plan (SAP).

